# **History of Protocol Versions**

Version	Date	Comments
1.0	20 December 2018	Internal version not submitted to the Health Authorities and the IEC/IRB
2.0	08 January 2019	Initial version submitted to the Health Authorities
3.0	15 March 2019	First approved version used in the study

## **Synopsis**

Company:	Sanofi Pasteur	
Investigational Product:	MenACYW conjugate vaccine	
Active Substance(s):	Capsular polysaccharide from meningococcal serogroups A, C, Y, and W conjugated to tetanus toxoid	
Title of the Study:	Immunogenicity and Safety of an Investigational Quadrivalent Meningococcal Conjugate Vaccine Versus Nimenrix® and NeisVac-C® in Healthy Toddlers 12 to 23 Months of Age	
Development Phase:	Phase III	
Coordinating Investigator:	This is a multi-center trial with multiple investigators.	
Study Sites:	This will be a multi-center, multi-country trial with approximately 31 trial centers in European countries.	
	Investigators and sites will be listed in the "List of Investigators and Centers Involved in the Trial" document.	
Planned Study Period:	3Q 2019 –4Q 2020	
Study Design, Schedule of Study Procedures, and Methodology:	This will be a Phase III, modified double-blind, randomized, parallel-groups, active-controlled, multi-center trial to compare the immunogenicity of a single dose of MenACYW conjugate vaccine to a single dose of a licensed quadrivalent meningococcal polysaccharide groups A, C, W-135, Y conjugate vaccine (MenACWY-TT, Nimenrix®) or of a licensed monovalent meningococcal group C conjugate vaccine (MenC-TT, NeisVac-C®) in toddlers, 12 to 23 months of age in Europe who are meningococcal vaccine naïve.	
	Vaccination	
	Approximately 705 healthy toddlers aged 12 to 23 months who have not received any meningococcal vaccine during infancy will be randomized in a 1:1:1 ratio to receive one dose of vaccine on Day (D) 0 (D0) at Visit 1 (V01) in one of the following 3 arms:	
	• Group 1: MenACYW conjugate vaccine (n=235)	
	• Group 2: Nimenrix® vaccine (MenACWY-TT conjugate vaccine) (n=235)	
	• Group 3: NeisVac-C® vaccine (MenC-TT conjugate vaccine) (n=235)	
	The randomization will be stratified by Center.	
	Blood sampling	
	All subjects will provide a pre-vaccination blood sample at V01 on D0 and a post-vaccination blood sample at Visit 2 (V02) (30 to 44 days after the vaccination at V01), for immunogenicity assessment.	
	Collection of safety data	
	- All subjects will be followed for safety from V01 on D0 to V02 after vaccination.	
	- All subjects will be observed for 30 minutes after vaccination and any unsolicited systemic adverse events (AEs) occurring during that time will be recorded as immediate unsolicited AEs in the electronic case report book (eCRB).	
	- The subject's parent or another legally acceptable representative will record information in a diary card about solicited reactions from D0 to D7 after vaccination and unsolicited AEs will be recorded from D0 to D30.	

- Serious adverse events (SAEs, including adverse events of special interest [AESIs]) will be recorded in a diary card throughout the study. The subject's parent / legally acceptable representative will be asked to notify the site immediately about any potential SAEs at any time during the study.
- Study site staff will contact subjects' parent / legally acceptable representative by telephone on 8 days (+ 2 days) after V01 to identify the occurrence of any SAEs (including AESIs) not yet reported and to remind them to complete the diary card and bring it back to V02.
- The completed diary card will be collected and reviewed with the subject's parent / legally acceptable representative at V02.

# Interruption of the Study:

The study may be discontinued if new data about the investigational product resulting from this study or any other studies become available; or for administrative reasons; or on advice of the Sponsor, the Investigators, the IECs (Independent Ethics Committees)/IRBs (Institutional Review Boards), or the governing regulatory authorities in the countries where the study is taking place.

There will be an internal team at the level of the Sponsor (Safety Management Team [SMT]), which will review the data being generated from all ongoing studies with MenACYW conjugate vaccine at regular intervals for any new safety signals or safety concerns. The SMT is empowered to recommend a pause in recruitment while it investigates any potential signal or concern.

If the study is prematurely terminated or suspended, the Sponsor shall promptly inform the Investigators, the IECs/IRBs, the regulatory authorities, and any contract research organization(s) used in the study of the reason for termination or suspension, as specified by the applicable regulatory requirements. The Investigator shall promptly inform the subjects' parents/legally acceptable representatives and should assure appropriate subject therapy and/or follow-up.

# Primary Objectives:

- To demonstrate the non-inferiority of the seroprotection rate (antibody titers ≥ 1:8) to meningococcal serogroup C following the administration of a single dose of MenACYW conjugate vaccine or Nimenrix® as measured by serum bactericidal assay using human complement (hSBA). If the non-inferiority of the seroprotection rate (antibody titers ≥ 1:8) is demonstrated, then
  - 1.1) To demonstrate the non-inferiority of the antibody response (geometric mean titers [GMT]) to meningococcal serogroup C following the administration of a single dose of MenACYW conjugate vaccine or Nimenrix® as measured by hSBA. If the non-inferiority of the antibody response (GMT) is demonstrated, then
  - 1.2) To demonstrate the superiority of the antibody response (GMT) to meningococcal serogroup C following the administration of a single dose of MenACYW conjugate vaccine or Nimenrix® as measured by hSBA. If the superiority of the antibody response (GMT) is demonstrated, then
  - 1.3) To demonstrate the superiority of the seroprotection rate to meningococcal serogroup C following the administration of a single dose of MenACYW conjugate vaccine or Nimenrix® as measured by hSBA.
- To demonstrate the non-inferiority of the seroprotection rate (antibody titers ≥ 1:8) to meningococcal serogroup C following the administration of a single dose of MenACYW conjugate vaccine or NeisVac-C® as measured by serum bactericidal assay using baby rabbit complement (rSBA). If the non-inferiority of the seroprotection rate is demonstrated, then
  - 2.1) To demonstrate the non-inferiority of the antibody response (GMT) to meningococcal serogroup C following the administration of a single dose of MenACYW conjugate vaccine or NeisVac-C® as measured by rSBA. If the non-inferiority of the antibody response (GMT) is demonstrated, then

	2.2) To demonstrate the superiority of the antibody response (GMT) to meningococcal serogroup C following the administration of a single dose of MenACYW conjugate vaccine or NeisVac-C® as measured by rSBA.  Overall, the primary objective for the study will be met if, objective 1) - non-inferiority of the seroprotection rate versus Nimenrix® as measured by hSBA, or objective 2) - non-inferiority of the seroprotection rate versus NeisVac-C® as measured by rSBA, is met.
Primary Endpoints:	
 
1) Antibody titers against meningococcal serogroup C measured by hSBA, 30 days (+ 14 days) after vaccination:
 
• ≥ 1:8, with MenACYW conjugate vaccine or Nimenrix®
 
• With MenACYW conjugate vaccine or Nimenrix®
 

	
 
2) Antibody titers against meningococcal serogroup C measured by rSBA, 30 days (+ 14 days) after vaccination:
 
≥ 1:8, with MenACYW conjugate vaccine or NeisVac-C®
 
With MenACYW conjugate vaccine or NeisVac-C®
 

Secondary Objectives:	To demonstrate the non-inferiority of the seroprotection rate (antibody titers ≥ 1:8) to meningococcal serogroup C following the administration of a single dose of MenACYW conjugate vaccine or Nimenrix® as measured by rSBA. If the non-inferiority of the seroprotection rate is demonstrated, then
	
 
1.1) To demonstrate the non-inferiority of the antibody response (GMT) to meningococcal serogroup C following the administration of a single dose of MenACYW conjugate vaccine or Nimenrix® as measured by rSBA. If the non-inferiority of the antibody response (GMT) is demonstrated, then
 
1.2) To demonstrate the superiority of the antibody response (GMT) to meningococcal serogroup C following the administration of a single dose of MenACYW conjugate vaccine or Nimenrix® as measured by rSBA
 

	2) To demonstrate the non-inferiority of the seroprotection rate (antibody titers ≥ 1:8) to meningococcal serogroup C following the administration of a single dose of MenACYW conjugate vaccine or NeisVac-C® as measured by hSBA. If the non-inferiority of the seroprotection rate is demonstrated, then
	
 
2.1) To demonstrate the non-inferiority of the antibody response (GMT) to meningococcal serogroup C following the administration of a single dose of MenACYW conjugate vaccine or NeisVac-C® as measured by hSBA. If the non-inferiority of the antibody response (GMT) is demonstrated, then
 
2.2) To demonstrate the superiority of the antibody response (GMT) to meningococcal serogroup C following the administration of a single dose of MenACYW conjugate vaccine or NeisVac-C® as measured by hSBA
 

	Overall, the secondary objective for the study will be met if objective 1) - non-inferiority of the seroprotection rate versus Nimenrix $^{\$}$ as measured by rSBA, or objective 2) - non-inferiority of the seroprotection rate versus NeisVac-C $^{\$}$ as measured by hSBA, is met.
Secondary Endpoints:	
 
1) Antibody titers against meningococcal serogroup C measured by rSBA,30 days (+ 14 days) after vaccination:
 
• ≥ 1:8, with MenACYW conjugate vaccine or Nimenrix®
 
• With MenACYW conjugate vaccine or Nimenrix®
 

	
 
2) Antibody titers against meningococcal serogroup C measured by hSBA, 30 days (+ 14 days) after vaccination:
 
• ≥ 1:8 with MenACYW conjugate vaccine or NeisVac-C®
 
• With MenACYW conjugate vaccine or NeisVac-C®
 

# Observational Objectives:

#### **Immunogenicity**

- 1) To describe the antibody response to meningococcal serogroup C before and 30 days (+ 14 days) after vaccination in each group using hSBA in toddlers
- 2) To describe the antibody response to meningococcal serogroup C before and 30 days (+ 14 days) after vaccination in each group using rSBA in toddlers

#### Safety

To describe the safety profile of MenACYW conjugate vaccine, Nimenrix® and NeisVac-C®.

# Observational Endpoints:

#### **Immunogenicity**

Observational Objective 1:

- Antibody titer against meningococcal serogroup C measured by hSBA in each group:
  - Assessed before and at 30 days (+ 14 days) after vaccination
  - $\geq$  1:4 and  $\geq$  1:8, assessed at 30 days (+ 14 days) after vaccination
  - $\geq$  4-fold rise from pre-vaccination to post-vaccination
  - Post-vaccination / pre-vaccination titer ratio
  - Vaccine seroresponse measured by hSBA\* in each group

with seroresponse defined as:

- For a subject with a pre-vaccination titer < 1.8, a post-vaccination titer  $\ge 1.16$
- For a subject with a pre-vaccination titer ≥ 1:8, a post-vaccination titer at least 4-fold greater that the pre-vaccination titer.

Observational Objective 2:

- Antibody titers against meningococcal serogroup C measured by rSBA in each group:
  - Assessed before and at 30 days (+ 14 days) after vaccination
  - $\geq 1.8$  and  $\geq 1.128$ , assessed before and at 30 days (+ 14 days) after vaccination
  - Post-vaccination / pre-vaccination titers ratio
  - ≥ 4-fold rise from pre-vaccination to post-vaccination
  - Vaccine seroresponse measured by rSBA, with seroresponse defined as:
    - For a subject with pre-vaccination titer < 1:8, a post-vaccination titer  $\ge 1:32$
    - For subjects with pre-vaccination titer ≥ 1:8, a post-vaccination titer at least 4-fold greater that the pre-vaccination titer

#### Safety

The safety profile of the 3 vaccines will be evaluated within 30 days (+ 14 days) after the vaccination. The following endpoints will be used for all subjects for the evaluation of safety:

- Unsolicited systemic AEs reported in the 30 minutes following the vaccination
- Solicited (pre-listed in the subject diary and the electronic Case Report Form [CRF])
  injection site reactions and systemic reactions starting anytime from D0 (Day of
  vaccination) through D7 after the vaccination
- Unsolicited (spontaneously reported) non-serious AEs up to from D0 and D30
- SAEs (including AESIs) throughout the study, ie, from D0 to Visit 2

Depending on the items, the endpoints recorded or derived could include:

Nature (Medical Dictionary for Regulatory Activities [MedDRA] preferred term), time of onset, duration / number of days of occurrence, intensity, relationship to vaccine, whether the AE led to early termination from the study, seriousness criterion, outcome.

Planned Sample Size:	A total of 675 subjects were initially planned to be enrolled (with an estimated drop-out rate of 10%).
	• Group 1: MenACYW conjugate vaccine n=225 to be enrolled (202 evaluable)
	• Group 2: Nimenrix® vaccine n=225 to be enrolled (202 evaluable)
	• Group 3: NeisVac-C® vaccine n=225 to be enrolled (202 evaluable)
	As a consequence of the COVID-19 pandemic, enrollment was paused on 17 March 2020.
	Approximately 30 subjects were identified to be excluded from the per-protocol analysis set
	(PPAS) due to COVID-19 as they were unable to complete their follow-up visit as planned per
	the protocol. The sample size of the study will then be modified to replace these subjects.
	Approximately 705 subjects will now be enrolled (235 in each group).
	In the event of any new unexpected situations impacting study visits, the sample size might be
	increased to replace subjects excluded from the PPAS.
Duration of	The duration of each subject's participation in the trial will be approximately 30 to 44 days.
Participation	
in the Study:	
Investigational Product:	MenACYW conjugate vaccine: Meningococcal Polysaccharide (Serogroups A, C, W, and Y) Tetanus Toxoid Conjugate Vaccine (Sanofi Pasteur Inc., Swiftwater, PA, USA)
Form:	Liquid solution
	Each 0.5 mL dose of MenACYW conjugate vaccine is formulated in sodium acetate buffered saline solution to contain the following components:
	Meningococcal capsular polysaccharides:
	Serogroup A10 micrograms (µg)
	Serogroup C
	Serogroup Y
	Serogroup W
	Tetanus toxoid protein carrier approximately 55 μg*
	* Tetanus toxoid protein quantity is approximate and dependent on the polysaccharide-to- protein ratio for the conjugates used in each formulation.
Route:	Intramuscular (IM)
Batch #	To be determined
Control Product:	Nimenrix®: Meningococcal polysaccharide groups A, C, W-135 and Y conjugate vaccine (Pfizer Limited, Sandwich, United Kingdom)
Form:	Lyophilized powder in a vial and diluent for reconstitution in a pre-filled syringe
Composition:	Each 0.5 mL dose of Nimenrix® vaccine is formulated to contain:
	Neisseria meningitidis polysaccharides:
	Serogroup A5 μg
	Serogroup C
	Serogroup V 5 μg
	Serogroup Y
	Tetanus toxoid protein carrierapproximately 44 µg
	Excipients: In the powder: Sucrose, Trometamol
	In the solvent: Sodium chloride, Water for injections
Route:	IM
Batch #	Commercial lot to be supplied by Sponsor
-	11 , 1

Control Product:	NeisVac-C®: Meningococcal Group C Polysaccharide Conjugate Vaccine Adsorbed (Pfizer Limited, Sandwich, United Kingdom)
Form:	Suspension for injection in pre-filled syringe
Composition:	Each 0.5 mL dose of NeisVac-C® vaccine is formulated to contain:
	Neisseria meningitidis serogroup C (strain C11) polysaccharide (de-O-acetylated) 10 μg conjugated to tetanus toxoid
Route:	IM
Batch #	Commercial lot to be supplied by Sponsor
Inclusion Criteria:	An individual must fulfill all of the following criteria in order to be eligible for study enrollment:
	1) Aged 12 to 23 months on the day of the first study visit
	2) Informed consent form (ICF) has been signed and dated by the parent(s) / legally acceptable representative(s)
	3) Subject and parent / legally acceptable representative are able to attend all scheduled visits and to comply with all study procedures
	4) Covered by health insurance if required by local regulations
Exclusion	An individual fulfilling any of the following criteria is to be excluded from study enrollment:
Criteria:	
 
Participation in the 4 weeks (28 days) preceding the study vaccination or planned participation during the present study period in another clinical study investigating a vaccine, drug, medical device, or medical procedure
 
Receipt of any vaccine in the 4 weeks (28 days) preceding the study vaccination or planned receipt of any vaccine prior to Visit 2 except for influenza vaccination, which may be received at least 2 weeks before or after study investigational vaccines. This exception includes monovalent pandemic influenza vaccines and multivalent influenza vaccines
 
Receipt of immune globulins, blood or blood-derived products in the past 3 months
 

	4) Previous vaccination against meningococcal disease with either the study vaccine or another vaccine (ie, mono- or polyvalent, polysaccharide, or conjugate meningococcal vaccine containing serogroups A, C, W, or Y; or meningococcal B vaccine)
	5) Known or suspected congenital or acquired immunodeficiency; or receipt of immunosuppressive therapy, such as anti-cancer chemotherapy or radiation therapy, within the preceding 6 months; or long-term systemic corticosteroid therapy (prednisone or equivalent for more than 2 consecutive weeks within the past 3 months)
	History of meningococcal infection, confirmed either clinically, serologically, or microbiologically
	7) At high risk for meningococcal infection during the study (specifically, but not limited to, subjects with persistent complement deficiency, with anatomic or functional asplenia, or subjects travelling to countries with high endemic or epidemic disease)
	8) Known systemic hypersensitivity to any of the vaccine components, or history of a life- threatening reaction to the vaccines used in the study or to a vaccine containing any of the same substances
	9) Personal history of an Arthus-like reaction after vaccination with a tetanus toxoid-containing vaccine

- 10) Personal history of Guillain-Barré syndrome (GBS)
- 11) Thrombocytopenia, as reported by the parent/ legally acceptable representative or suspected thrombocytopenia contraindicating intramuscular vaccination in the Investigator's opinion
- 12) Bleeding disorder, or receipt of anticoagulants in the 3 weeks preceding inclusion, contraindicating intramuscular vaccination in the Investigator's opinion
- 13) Chronic illness that, in the opinion of the Investigator, is at a stage where it might interfere with study conduct or completion
- 14) Moderate or severe acute illness/infection (according to Investigator judgment) on the day of vaccination or febrile illness (temperature ≥ 38.0°C). A prospective subject should not be included in the study until the condition has resolved or the febrile event has subsided.
- 15) Receipt of oral or injectable antibiotic therapy within 72 hours prior to the first blood draw
- 16) Identified as a natural or adopted child of the Investigator or employee with direct involvement in the proposed study

# Statistical Methods:

#### **Primary Objective**

The immunogenicity of MenACYW conjugate vaccine serogroup C will be compared to that of Nimenrix® vaccine and to that of NeisVac-C® vaccine using sequential testing approaches.

#### Non-Inferiority

A non-inferiority testing approach will be used to compare post-vaccination (ie, 30 days after the vaccination) seroprotection rates and GMTs of MenACYW conjugate vaccine to that of Nimenrix® and NeisVac-C®, using a two-sided 95% Confidence Interval (CI) with the following hypotheses:

For seroprotection rates:

$$H_0: \pi_{\text{MenACYW}} - \pi_{\textit{Comparator}} \leq -0.1$$

$$H_1: \pi_{\text{MenACYW}} - \pi_{\textit{Comparator}} > -0.1$$

Or

For GMTs

$$H_0: GMT_{MenACYW}/GMT_{Comparator} \leq 1/\delta$$

$$H_1: GMT_{MenACYW}/GMT_{Comparator} > 1/\delta$$

with:

- Comparator: Nimenrix® or NeisVac-C®
- $\pi$ : seroprotection rates
- δ: non-inferiority margin set at 1.5

#### Superiority

If the non-inferiority testing succeeds then a superiority approach will be used to compare post-vaccination (ie, 30 days after the vaccination) seroprotection rates and/or GMTs of MenACYW conjugate vaccine to that of Nimenrix® and NeisVac-C®, using a two-sided 95% CI with the following hypotheses:

For seroprotection rates

 $H_0: \pi_{\text{MenACYW}} - \pi_{\text{Comparator}} \leq 0$ 

 $H_1: \pi_{\text{MenACYW}} - \pi_{comparator} > 0$ 

Or

For GMTs

 $H_0: GMT_{MenACYW}/GMT_{Comparator} \leq 1$ 

 $H_1: GMT_{MenACYW}/GMT_{Comparator} > 1$ 

with:

- Comparator: Nimenrix® or NeisVac-C®
- $\pi$ : seroprotection rates

For the seroprotection rates, the 95% CI of the difference in proportions will be computed using the Wilson Score method without continuity correction (Newcombe method).

For the GMTs, the two-sided 95% CI of the ratio of post-vaccination GMTs will be calculated using normal approximation of log-transformed titers.

The non-inferiority will be demonstrated against seroprotection rates if the null hypothesis is rejected, ie, if the lower limit of the two-sided 95% CI for the difference between the seroprotection rates is > -10%.

The non-inferiority will be demonstrated against GMTs if the null hypothesis is rejected, ie, lower limit of the two-sided 95% CI for the ratio of GMTs > 1/1.5.

The superiority will be demonstrated against seroprotection rates if the null hypothesis is rejected, ie, if the lower limit of the two-sided 95% CI for the difference between the seroprotection rates is > 0%.

The superiority will be demonstrated against GMTs if the null hypothesis is rejected, ie, lower limit of the two-sided 95% CI for the ratio of GMTs > 1.

[figure not shown]
The testing approach will be done in parallel and using a step by step approach for the 2 comparators:

Nimenrix®:

If the non-inferiority using seroprotection rates of MenACYW conjugate vaccine against Nimenrix® measured by hSBA is demonstrated then the non-inferiority using hSBA GMTs will be tested. If the non-inferiority using hSBA GMTs of MenACYW conjugate vaccine against Nimenrix® is demonstrated then the superiority using hSBA GMTs will be tested. If the superiority using hSBA GMTs is demonstrated then the superiority using hSBA seroprotection rates will be tested.

Neis Vac- $C^{\mathbb{R}}$ :

If the non-inferiority using seroprotection rates of MenACYW conjugate vaccine against NeisVac-C® measured by rSBA is demonstrated then the non-inferiority using rSBA GMTs will be tested. If the non-inferiority using rSBA GMTs is demonstrated then the superiority using rSBA GMTs will be tested.

To conclude, non-inferiority using seroprotection rates of MenACYW conjugate vaccine against Nimenrix® measured by hSBA or non-inferiority using seroprotection rates of MenACYW conjugate vaccine against NeisVac-C® measured by rSBA have to be demonstrated.

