#### Calculation of Sample Size:

To complete the primary objective a total of 675 subjects were initially planned to be enrolled according to a ratio 1:1:1 (MenACYW: Nimenrix®: NeisVac-C®). This sample size will provide acceptable global powers considering an overall one-sided alpha of 2.5% (ie, 1.25% adjusted alpha for each of the 2 main non-inferiority tested, then same level of alpha is used for the subsequent tests as a ranking testing strategy is used), an initial drop-out rate of 10% (ie, 202 evaluable subjects per group; not taking into account the impact of COVID-19) and based on the following additional hypotheses:

Objective number	Step	Comparator	Statistical test	Endpoint	Ref. MenACYW vs Comparator	Clinical margin	Standard deviation (SD)	Indivi- dual power	Sequential power
1	1	Nimenrix hSBA	NI	Seroprote ction rates	98% vs 88%	10%		>99.9%	>99.9%
	2	Nimenrix hSBA	NI	GMTs	GMTR=1.5	1.5	0.5	>99.9%	>99.9%
	3	Nimenrix hSBA	Sup	GMTs	GMTR=1.5	-	0.5	90.1%	89.9%
	4	Nimenrix hSBA	Sup	Seroprote ction rates	98% vs 88%	10%		95.8%	86.1%
2	1	Neisvac-C rSBA	NI	Seroprote ction rates	98% vs 98%	10%		>99.9%	>99.9%
	2	Neisvac-C rSBA	NI	GMTs	GMTR=1	1.5	0.5	90.1%	90.1%
	3	Neisvac-C rSBA	Sup	GMTs	GMTR=1.5	-	0.5	90.1%	81.2%

NI: non-inferiority; Sup: superiority

GMTR: Geometric Mean of Titers ratios of MenACYW vs Comparator

One-sided Alpha of 1.25% used for all calculations

Sequential power correspond to the overall power of each step of the statistical tests to be performed

Reference seroresponse rates and SDs made from Phase II and III toddler studies MET51, MET32 and MET54.

In addition, considering such sample size will also provide acceptable global powers to achieve the secondary objective, considering an overall one-sided alpha of 2.5% (ie, 1.25% adjusted alpha for each of the 2 main non-inferiority tested, then same level of alpha is used for the subsequent tests as a ranking testing strategy is used), an initial drop-out rate of 10% (not taking into account the impact of COVID-19), and based on the following additional hypotheses:

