# Non-Inferiority

A non-inferiority testing approach will be used to compare post-vaccination (ie, 30 days after the vaccination) seroprotection rates and GMTs of MenACYW conjugate vaccine to that of Nimenrix® and NeisVac-C®, using a two-sided 97.5% Confidence Interval (CI) with the following hypotheses:

For seroprotection rates:

$$H_0: \pi_{\text{MenACYW}} - \pi_{\text{Comparator}} \leq -0.1$$

$$H_1: \pi_{\text{MenACYW}} - \pi_{\textit{Comparator}} > -0.1$$

Or

For GMTs

$$H_0: GMT_{MenACYW}/GMT_{Comparator} \le 1/\delta$$

$$H_1: GMT_{MenACYW}/GMT_{Comparator} > 1/\delta$$

with:

- Comparator: Nimenrix® or NeisVac-C®
- $\pi$ : seroprotection rates
- $\delta$ : non-inferiority margin set at 1.5

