# **Superiority**

If the non-inferiority testing succeeds then a superiority approach will be used to compare post-vaccination (ie, 30 days after the vaccination) seroprotection rates and/or GMTs of MenACYW conjugate vaccine to that of Nimenrix® and NeisVac-C®, using a two-sided 97.5% CI with the following hypotheses:

For seroprotection rates

$$H_0: \pi_{\text{MenACYW}} - \pi_{\textit{Comparator}} \leq 0$$

$$H_1: \pi_{\text{MenACYW}} - \pi_{\textit{Comparator}} > 0$$

Or

For GMTs

$$H_0: GMT_{\text{MenACYW}} / GMT_{comparator} \le 1$$

$$H_1: GMT_{MenACYW}/GMT_{Comparator} > 1$$

with:

- Comparator: Nimenrix® or NeisVac-C®
- $\pi$ : seroprotection rates

For the seroprotection rates, the 97.5% CI of the difference in proportions will be computed using the Wilson Score method without continuity correction (Newcombe method).

For the GMTs, the two-sided 97.5% CI of the ratio of post-vaccination GMTs will be calculated using normal approximation of log-transformed titers.

The non-inferiority will be demonstrated against seroprotection rates if the null hypothesis is rejected, ie, if the lower limit of the two-sided 97.5% CI for the difference between the seroprotection rates is > -10%.

The non-inferiority will be demonstrated against GMTs if the null hypothesis is rejected, ie, lower limit of the two-sided 97.5% CI for the ratio of GMTs > 1/1.5.

The superiority will be demonstrated against seroprotection rates if the null hypothesis is rejected, ie, if the lower limit of the two-sided 97.5% CI for the difference between the seroprotection rates is > 0%.

The superiority will be demonstrated against GMTs if the null hypothesis is rejected, ie, lower limit of the two-sided 97.5% CI for the ratio of GMTs > 1.

The testing approach will be done in parallel and using a step by step approach for the 2 comparators (3 steps):

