#### **5.1.1.2** Statistical Methods

For the seroprotection rates, the 97.5% CI of the difference in proportions will be computed using the Wilson Score method without continuity correction (Newcombe method).

For the GMTs, the two-sided 97.5% CI of the ratio of post-vaccination GMTs will be calculated first using normal approximation of log-transformed titers and then by taking the antilogarithms of the lower and upper limits of the provided 97.5% CI.

The non-inferiority will be demonstrated against seroprotection rates if the null hypothesis is rejected, i.e., if the lower limit of the two-sided 97.5% CI for the difference between the seroprotection rates is > -10%.

The non-inferiority will be demonstrated against GMTs if the null hypothesis is rejected, i.e., lower limit of the two-sided 97.5% CI for the ratio of GMTs > 1/1.5.

The superiority will be demonstrated against seroprotection rates if the null hypothesis is rejected, i.e., if the lower limit of the two-sided 97.5% CI for the difference between the seroprotection rates is > 0%.

The superiority will be demonstrated against GMTs if the null hypothesis is rejected, i.e., lower limit of the two-sided 97.5% CI for the ratio of GMTs > 1.

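### The Synopsis judges every primary test on a two-sided 95% CI, while Section 12, the SAP and the power tables use 97.5% (one-sided 1.25%); applied as written, the Synopsis rule roughly doubles the type I error

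*Protocol*

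**What the plan says.** **Protocol Synopsis, Statistical Methods.** The non-inferiority comparison is set up "using a two-sided 95% Confidence Interval (CI) with the following hypotheses", and the superiority comparison likewise. The two sentences on how the intervals are computed (Newcombe for rates, log-normal for the GMT ratio) also say 95%, or refer to it. The decision rules follow:

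- Non-inferiority on rates: "if the lower limit of the two-sided 95% CI for the difference between the seroprotection rates is > -10"%.
- Non-inferiority on GMTs: "lower limit of the two-sided 95% CI for the ratio of GMTs > 1/1.5".
- Superiority on rates: "if the lower limit of the two-sided 95% CI for the difference between the seroprotection rates is > 0"%.
- Superiority on GMTs: same form, 95% CI, ratio above 1.

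The secondary objectives in the Synopsis are said to follow a similar approach, so they inherit the 95% level.

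**Protocol Section 12.1.1.2.** The same tests are set up "using a two-sided 97.5% Confidence Interval (CI) with the following hypotheses", and non-inferiority on rates is shown "if the lower limit of the two-sided 97.5% CI for the difference between the seroprotection rates is > -10"%.

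**SAP Sections 5.1.1.1, 5.1.1.2 and 5.1.2.2.** These use 97.5% throughout, for example "lower limit of the two-sided 97.5% CI for the ratio of GMTs > 1/1.5", and again for the secondary objectives.

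**Synopsis, Calculation of Sample Size, and SAP Section 5.5.** Overall one-sided alpha is 2.5%, split as 1.25% for each of the two leading non-inferiority tests. The power-table footnote reads "One-sided Alpha of 1.25% used for all calculations".

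**Success rule (Protocol Section 2.1, SAP Section 2.1).** The primary objective is met if non-inferiority of seroprotection is shown against either Nimenrix (hSBA) or NeisVac-C (rSBA).

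**The concern.** The either/or success rule gives the trial two chances to win. Holding the overall one-sided error at 2.5% therefore needs a split, and the plan chose 1.25% per comparator. A two-sided 97.5% CI delivers that split. A two-sided 95% CI spends the full 2.5% on each comparator, so the Synopsis rules contradict the alpha statement in the Synopsis's own sample-size section as well as Section 12 and the SAP.

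This is the threshold for the primary claim, and for every step that follows it in each sequence. A result between the two thresholds would be a success under one part of the approved protocol and a failure under another. The documents supplied contain no clause saying which section prevails. The Synopsis is current text: it already carries the COVID-19 increase to 705 subjects. SAP Section 5.7, which lists changes to the planned analyses, does not mention the interval level.

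**Working it through.** **Inputs from the documents.** 202 evaluable per group; SD 0.5 (taken as log10 scale); GMT margin 1.5; rate margin 10 points; planning rates 98% vs 88% and 98% vs 98%; one-sided alpha 1.25% per comparator. The correlation between the two leading tests (shared MenACYW arm, different assays) is not given, so I take 0 to 0.75 as an assumed range.

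**1. Which level do the plan's powers use?**

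Standard error of the log10 GMT difference: 0.5 × √(2/202) = 0.04975. Effect: log10(1.5) = 0.1761. Noncentrality: 0.1761/0.04975 = 3.539, with 402 df. For rate superiority I used the pooled-variance normal approximation.

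| Test | Stated power | At one-sided 1.25% | At one-sided 2.5% |
|---|---|---|---|
| GMT (superiority at ratio 1.5, or non-inferiority at ratio 1) | 90.1% | 90.1% | 94.2% |
| Superiority of rates, 98% vs 88% | 95.8% | 95.8% | 97.8% |

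The two-step power also agrees: 0.901 × 0.901 = 81.2%, as stated. The design level is one-sided 1.25%, which is the two-sided 97.5% CI.

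**2. Chance of at least one false non-inferiority claim.** Both nulls are true at their margins, and the test statistics are bivariate normal with correlation ρ. The error is 1 − P(Z1 < c, Z2 < c), where c is the 0.975 or 0.9875 normal quantile. At ρ = 0 this is 1 − (1 − α)²: 1 − 0.975² = 4.94%, and 1 − 0.9875² = 2.48%.

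| ρ | 95% CI (Synopsis) | 97.5% CI (Section 12, SAP) |
|---|---|---|
| 0 | 4.94% | 2.48% |
| 0.25 | 4.80% | 2.44% |
| 0.5 | 4.54% | 2.32% |
| 0.75 | 4.05% | 2.09% |

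The ratio of the two columns is 1.94 to 1.99 throughout. Whatever the correlation, the upper bounds are 2 × 2.5% = 5.0% and 2 × 1.25% = 2.5%.

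The Newcombe interval is close to these nominal levels. The exact size of one rate non-inferiority test with 202 per arm is 2.34% (95%) against 1.13% (97.5%) for true rates 88% vs 98%, and 2.58% against 1.29% for 78% vs 88%.

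**3. GMT results on which the two rules disagree.** The t quantiles on 402 df are 1.966 and 2.250; multiplied by 0.04975 they give 0.0978 and 0.1119.

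- Non-inferiority, smallest passing observed ratio: 10^(−0.1761 + 0.0978) = 0.835 at 95%; 10^(−0.1761 + 0.1119) = 0.863 at 97.5%.
- Superiority: 10^0.0978 = 1.253 at 95%; 10^0.1119 = 1.294 at 97.5%.

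With normal quantiles, the figures are 0.834/0.862 and 1.252/1.293.

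**4. The seroprotection test that decides the primary objective.** Newcombe lower limit: d − √[(p1 − l1)² + (u2 − p2)²], where l1 is the Wilson lower limit for MenACYW and u2 the Wilson upper limit for the comparator. As an illustration, take 188/202 vs 198/202, so p1 = 0.9307, p2 = 0.9802, d = −0.0495.

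- 95%: l1 = 0.8870, u2 = 0.9923; limit = −0.0495 − √(0.0437² + 0.0121²) = −9.5%, a pass.
- 97.5%: l1 = 0.8793, u2 = 0.9932; limit = −0.0495 − √(0.0514² + 0.0130²) = −10.2%, a fail.

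With the comparator at 198/202, the fewest MenACYW responders that pass are 188 (95%) and 189 (97.5%). With the comparator at 178/202, they are 172 and 174.

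**The case against.** The best defence is that the intended level is not in doubt. Section 12.1.1.2, SAP Sections 5.1.1.1, 5.1.1.2, 5.1.2.2 and 5.5, and the Synopsis's own sample-size text all point to 97.5% or one-sided 1.25%. Protocol Section 12.1 hands the description of all analyses to the SAP, and the SAP has no confirmatory 95% rule. If the analysts follow the SAP, alpha is controlled.

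This much of it stands:

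- The inflation is conditional. It occurs only if the Synopsis rule is applied.
- The leading seroprotection test is unlikely to be borderline. Under the planning rates, the chance that the two rules disagree there is about 0.016% (98% vs 98%) and effectively zero (98% vs 88%).
- The GMT windows matter mainly for NeisVac-C. Against Nimenrix by hSBA, Protocol Section 1.2.1.2 reports a serogroup C GMT ratio of 16.5 in vaccine-naïve toddlers, far from 1.25–1.29. The protocol's background section gives no earlier GMT ratio against NeisVac-C.
- The 4.5–4.9% range needs both nulls true at their margins together, and a correlation that the documents do not supply.

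These points limit how likely harm is. They do not remove the contradiction: a reader of the Synopsis would take 95% as the prespecified threshold, and nothing in the documents supplied says that another section overrides it.

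**Conclusion.** The concern holds. The Synopsis states the wrong interval level for all four primary decision rules, and by reference for the secondary ones. The per-test one-sided error under its wording is exactly twice the planned level (2.5% against 1.25%). The error for the either/or primary objective is about 1.9 to 2.0 times that of the 97.5% rule: 4.5–4.9% against 2.3–2.5% for correlations from 0.5 to 0.

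The practical exposure lies mostly in the GMT steps, powered at about 90%, where observed ratios of 0.835–0.863 or 1.253–1.294 are read in opposite ways. These cut-offs assume 202 per arm and an observed log10 SD of 0.5. Because the point concerns the primary success threshold of a confirmatory trial, it must be corrected, even though the intended level is clear.

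**What to change.** In the Synopsis, Statistical Methods, replace 95% by 97.5% in every confirmatory statement: the set-up of the non-inferiority and superiority comparisons, the Newcombe and GMT-ratio interval sentences, and all four decision rules. The secondary objectives then inherit the right level. Keep 95% for the descriptive intervals of the observational objectives (Synopsis, Protocol Section 12.1.3, SAP Section 5.1.3).

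The cost is a wording change in the Protocol, processed as an amendment under Section 5.3, where even a non-substantial amendment must be notified to the ethics committees. No subjects, new analyses or power recalculation are needed, because the stated powers were already computed at one-sided 1.25%. Section 12.1.1.2 and the SAP need no change on this point.
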